8.3 Adverse Events and Serious Adverse Events

8.3.1 Definition of Adverse Event (AE)

AE means any untoward medical occurrence associated with the use of an intervention in humans, whether or not considered intervention related. An AE can therefore be any unfavorable and unintended sign (including an abnormal laboratory finding), symptom, or disease temporally associated with the use of medicinal (investigational) product. If multiple abnormalities are part of the same clinical syndrome, they can be reported together as one AE under a unifying clinical diagnosis.

Any medical condition that is present at the time that the subject is screened will be considered as baseline and not reported as an AE. However, if the severity of any pre-existing (baseline) medical condition increases above baseline to severity grade 3 or 4, it should be recorded as an AE.

Given the nature of severity of the underlying illness, subjects will have many symptoms and abnormalities in vital signs and laboratory values. Only Grade 3 and 4 AEs will be captured in this trial. In addition, the following AEs will be reported:

- Any Grade 2 or higher suspected drug-related hypersensitivity reactions associated with study product administration will be reported as an AE.
- Any venous thromboembolism at any time during the study.

Unsolicited-laboratory values collected as part of standard of care, will need to be reported only if Grade 3 or above and only if clinically significant and/or part of a diagnosis or a clinical syndrome. In this case, if laboratory and vital sign abnormalities are part of the clinical syndrome, they should be reported as one AE under one clinical diagnosis or syndrome. Example: Low oxygen level/arterial blood gases could be part of respiratory failure diagnosis.

Intermittent abnormal laboratory values or vital sign measurements common in the severely ill populations (such as electrolyte abnormalities, low blood pressure, hyperglycemia, etc.) that are part of the same clinical diagnosis (e.g., uncontrolled diabetic) can be recorded once with the worst grade for each adverse event (grade 3 and 4 only for this trial), with the start and stops dates of the intermittent syndrome. If there is clear resolution of the event, and then recurrence, it should be treated as a separate adverse event. Resolution is defined as return to baseline (either

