8.3.4.1 Severity of Adverse Events

All AEs and SAEs will be assessed for severity using the DAIDS Table for Grading the Severity of Adult and Pediatric Adverse Events, version 2.1 (July 2017).

For AEs not included in the Table, the following guidelines will be used to describe severity. In addition, all deaths related to an AE are to be classified as grade 5 according to the DAIDS Table.

- Moderate (Grade 2): Events that are usually alleviated with additional specific therapeutic intervention. The event interferes with usual activities of daily living and causes discomfort but poses no significant or permanent risk of harm to the research subject.
- Severe (Grade 3): Events that interrupt usual activities of daily living, or significantly affect clinical status, or may require intensive therapeutic intervention. Severe events are usually incapacitating.
- Potentially life-threatening event (Grade 4): Events that are potentially life threatening.
- Deaths (Grade 5): All deaths related to an AE are classified as grade 5 (per DAIDS Table).

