8.3.5 Time Period and Frequency for Event Assessment and Follow-Up

For this study, all Grade 3 and 4 AEs, all SAEs occurring from the time the informed consent is signed through the Day 29 visit will be documented, recorded, and reported.

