9.3. Adverse Events

For the calculation of incidence of adverse events (i.e., on a per subject basis), each subject will only be counted once and any repetitions of adverse events within a subject will be ignored; the denominator will be the number of subjects in the Treated population. All adverse events reported will be included in the summaries and analyses.

An overall summary by treatment arm and disease severity of adverse events is presented that includes, but not limited to: subjects with at least one event, at least one related event, at least one SAE, at least one related SAE and at least one AE leading to early termination (Table 56 and Table 57).

Adverse events occurring in 5% of subjects (by MedDRA preferred term) in any treatment group will be presented (Table 58).

The proportion of subjects reporting at least one adverse event will be summarized by MedDRA system organ class and preferred term for each treatment arm, disease severity and overall. Denominators for percentages are the number of subjects in the Treated population.

The following summaries for adverse events will be presented by MedDRA system organ class, preferred term, disease severity and treatment group:

- Treatment-emergent renal adverse events by preferred term (Table 61);
- Treatment-emergent hepatic adverse events by preferred term (Table 62);
- Related adverse events by MedDRA system organ class and preferred term (Table 63);
- Subject listing of non-serious adverse events (Listing 11);
- Bar chart of non-serious related adverse events by severity and MedDRA system organ class (Figure 37);
- Bar chart of non-serious related adverse events by maximum severity and MedDRA system organ class (Figure 40);

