Rates of Grade 3 and 4 AE occurrence will be compared between treatment arms using Barnard's exact test and presented. Rates of SAE occurrence will also be compared between treatment arms using Barnard's exact test and presented. Further, the composite endpoint of the occurrence of death, SAE, or Grade 3 or 4 AE described in Section 3.3 will be analyzed as a time to event outcome. A table will present median time to event along with 95% confidence intervals overall for each treatment arm along with the hazard ratio estimate and log rank p-values (Table 73). Differences in time-to-event endpoints by treatment will be summarized with Kaplan-Meier curves.

A summary of the infections reported on the AE CRF will be summarized by treatment group and disease severity (Table 74). The anatomical location(s) of the infection and causative pathogen(s) determined by culture will be summarized. Infections considered to be opportunistic, as identified by the sponsor, will also be included in the summaries.

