This table will only include the Treatment Group and HR columns only as well as a column to the left of Treatment Group titled “Interaction”. Two models will be run: “Treatment – Randomized Disease Severity” will include a treatment*randomized disease severity interaction term. “Treatment – Baseline Ordinal Score” will include a treatment*baseline ordinal score interaction term. For each interaction model, the p-value for the interaction term will be provided in a footnote reading “The p-value for the treatment by [randomized disease severity/baseline ordinal score] interaction term was 0.xxxx.”.

Table 71: Time to Death through Day 15 and 29 by Treatment Group: Restricted Mean Survival Time Analysis – ITT Population

Study Day	Treatment Group	Randomized Disease Severity	n	Restricted Mean Recovery Time		Difference	
				Estimate	95% CI	Estimate	95% CI
Day 15	Baricitinib + RDV (N=X)	Moderate	x	x.X	x.X, x.X	x.XX	x.XX, x.XX
	Placebo + RDV (N=X)		x	x.X	x.X, x.X		
	Baricitinib + RDV (N=X)	Severe	x	x.X	x.X, x.X	x.XX	x.XX, x.XX
	Placebo + RDV (N=X)		x	x.X	x.X, x.X		
	Baricitinib + RDV (N=X)	Any Severity	x	x.X	x.X, x.X	x.XX	x.XX, x.XX
	Placebo + RDV (N=X)		x	x.X	x.X, x.X		
Day 29	Baricitinib + RDV (N=X)	Moderate	x	x.X	x.X, x.X	x.XX	x.XX, x.XX
	Placebo + RDV (N=X)		x	x.X	x.X, x.X		
	Baricitinib + RDV (N=X)	Severe	x	x.X	x.X, x.X	x.XX	x.XX, x.XX
	Placebo + RDV (N=X)		x	x.X	x.X, x.X		
	Baricitinib + RDV (N=X)	Any Severity	x	x.X	x.X, x.X	x.XX	x.XX, x.XX
	Placebo + RDV (N=X)		x	x.X	x.X, x.X		

N= Number of subjects in the specified treatment group, disease severity, and analysis population.

n = Number of subjects who died by the specified study day.

Difference is the difference in the restricted mean mortality time between Baricitinib + RDV and Placebo + RDV.

Table 72: Subjects Experiencing Grade 3 or 4 AEs and SAEs through Day 29 by Treatment Group and Actual Disease Severity – As Treated Population

Safety Event Outcome	Baricitinib + RDV			Placebo + RDV			P-value
	n	%	95% CI	n	%	95% CI	
Any Severity (N = X)							
Grade 3 or 4 AE	x	x	x.x, x.x	x	x	x.x, x.x	0.xxx
SAE	x	x	x.x, x.x	x	x	x.x, x.x	0.xxx
Moderate (N = X)							
Grade 3 or 4 AE	x	x	x.x, x.x	x	x	x.x, x.x	0.xxx
SAE	x	x	x.x, x.x	x	x	x.x, x.x	0.xxx
Severe (N = X)							
Grade 3 or 4 AE	x	x	x.x, x.x	x	x	x.x, x.x	0.xxx
SAE	x	x	x.x, x.x	x	x	x.x, x.x	0.xxx

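### The Grade 3–4 AE comparison leaves out Grade 5, so a treated subject whose only AE record is fatal counts as having no event

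*SAP*

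**What the plan says.** SAP 9.4 (Deaths, Serious Adverse Events and other Significant Adverse Events) commits to a test: "Rates of Grade 3 and 4 AE occurrence will be compared between treatment arms", using Barnard's exact test. The shell is Table 72, "Subjects Experiencing Grade 3 or 4 AEs and SAEs through Day 29 by Treatment Group and Actual Disease Severity". It has two rows per severity group, Grade 3 or 4 AE and SAE, each with a CI and a p-value. Table 57 gives a risk difference and CI for Grade 3-4 AE and for Grade 3-4 related AE. Table 56 has the corresponding descriptive rows.

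Protocol Appendix B 8.3.4.1 takes the grading scale one step further: "All deaths related to an AE are classified as grade 5 (per DAIDS Table"). The SAP keeps that grade apart from Grades 3 and 4. Table 56 has its own Grade 5 rows, and Table 74 has separate severe, life-threatening and death columns. No text folds Grade 5 into the Grade 3–4 count.

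Two more rules matter. Appendix B 8.3.5 requires recording of "all Grade 3 and 4 AEs, all SAEs occurring from the time the informed consent is signed through the Day 29 visit", so a fatal AE enters the database as an SAE. SAP 9.3 counts by subject: "each subject will only be counted once and any repetitions of adverse events within a subject will be ignored". The cumulative incidence of Grade 3 and 4 AEs through Day 29 is a named secondary safety objective (Appendix B section 3; SAP 3.1).

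**The concern.** A programmer who follows these shells will filter on Grades 3 and 4. A treated subject with one AE record, respiratory failure ending in death and graded 5, then falls outside the numerator but stays in the denominator. Had the event stopped at Grade 4, the subject would have counted. On this line the outcome improves when a life-threatening event becomes fatal.

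Single fatal records are plausible. Appendix B 8.3.5.1 tells sites to group related signs, symptoms and test results under one diagnosis, and each AE is described with its severity. A deterioration that ends in death may therefore be entered once, as Grade 5.

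At stake is how the Grade 3–4 rate, its risk difference and its p-value are read. Protocol Appendix B 9.4.4 asks for the safety components to be analysed singly as well as in a composite, so this line will be read by itself.

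**Working it through.** The documents give no Grade 3–4 AE rate, difference or power, so there is no stated figure to reproduce. The check is on direction and possible size.

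**Inputs**
- Arm size: SAP section 5 gives a total of 1032 (723/0.70 = 1033, which agrees apart from rounding) and SAP 4.2.3 gives 1:1 allocation, so 516 per arm. The As Treated population may be slightly smaller.
- Death risk d: 11.6% and 8.0%, the ACTT-1 preliminary figures in SAP section 2. Their use for ACTT-2 is an assumption, made only for illustration.
- s, the risk of a Grade 3 or 4 AE among survivors, taken as equal in the two arms. Assumption, 20% to 50%.
- f, the share of decedents who also have a separate Grade 3 or 4 record, taken as equal in the two arms. Assumption, 0 to 100%.
- Every death is taken to have a Grade 5 AE record. Assumption.

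**Formulas**
- Rate as planned (Grade 3–4): s(1 − d) + f·d
- Rate with Grade 5 counted: s(1 − d) + d
- Difference as planned, more deaths minus fewer: (f − s) × (11.6 − 8.0) = (f − s) × 3.6 points
- Difference with Grade 5 counted: (1 − s) × 3.6 points
- Shrinkage: (1 − f) × 3.6 points, at most 3.6 (when f = 0)

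The planned difference is negative, meaning that the arm with more deaths looks better, exactly when f < s.

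**Difference as planned, in points**

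| s | f = 0 | f = 25% | f = 50% | f = 75% | f = 100% (same as counting Grade 5) |
|---|---|---|---|---|---|
| 20% | −0.7 | +0.2 | +1.1 | +2.0 | +2.9 |
| 30% | −1.1 | −0.2 | +0.7 | +1.6 | +2.5 |
| 40% | −1.4 | −0.5 | +0.4 | +1.3 | +2.2 |
| 50% | −1.8 | −0.9 | 0.0 | +0.9 | +1.8 |

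**Worked counts at s = 30%, f = 0, 516 per arm**
- Deaths: 60 vs 41.
- Grade 3–4 as planned: 137 (26.6%) vs 142 (27.5%), Barnard p = 0.74.
- Grade 5 counted: 197 (38.2%) vs 183 (35.5%), Barnard p = 0.37.

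The order changes. Neither comparison is near significance, so the effect here is on the direction and size of the estimate.

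**The case against.** The strongest reply is that fatal events are well covered elsewhere. An AE resulting in death is an SAE (Appendix B 8.3.2), and SAEs get their own Barnard test in the adjacent row of Table 72. The composite of death, SAE or Grade 3/4 AE is analysed as time to event (Table 73), and mortality has Kaplan-Meier rates, hazard ratios and log-rank tests (SAP 9.4). Table 57 has a row for SAEs with fatal outcome. Its AE row is also close to Grade 3 or higher already, because apart from Grade 3 and 4 AEs the trial captures only SAEs, suspected drug-related hypersensitivity of Grade 2 or above, and venous thromboembolism (Appendix B 8.3.1, 8.3.5). No decision rule hangs on the Grade 3–4 p-value. All of this stands. A reader might infer that excess deaths could be hidden from the safety evaluation; the documents do not support that. These analyses nevertheless leave the Grade 3–4 line as it is. The SAE rate is no substitute, since Appendix B 8.3.2 says that Grade 4 events need not be SAEs.

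Three other strong readings also fail:
- **All fatal cases drop out.** Counting is by subject, so only decedents with no other Grade 3 or 4 record are lost. Laboratory AEs count and laboratory tests are scheduled on Days 3, 5, 8 and 11 in hospital, so many decedents may have one. Against that, Appendix B 8.3.5.1 folds laboratory findings into the syndrome they belong to. The documents do not settle f.
- **A Grade 4 record is overwritten by Grade 5.** The rule that events "can be recorded once with the worst grade for each adverse event" concerns intermittent laboratory or vital-sign abnormalities and is limited there to Grades 3 and 4.
- **The arm with more deaths will generally look safer.** One could fix the Grade 3 or higher rate at, say, 45% in both arms and subtract unrecorded deaths. That forces unequal survivor risk: if no decedent has a lower-grade record counted, (45 − 8.0)/92.0 = 40.2% vs (45 − 11.6)/88.4 = 37.8%. Part of the apparent bias would then be a real difference in non-fatal events. With equal survivor risk, reversal needs f < s.

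**Conclusion.** The point holds for the Grade 3–4 line only: the test in SAP 9.4 and Table 72, and the Grade 3–4 rows of Tables 56 and 57. As defined, that line understates the arm with more deaths by (1 − f) times the mortality difference, at most 3.6 points if the ACTT-1 death risks applied and f were the same in both arms. The usual effect is attenuation. Reversal is possible but depends on f being smaller than s, and both are unknown. The direction follows from the definitions; the size rests on the assumptions. The primary analysis is untouched. This is a cheap improvement worth making, because a compared safety outcome should not improve when an event turns fatal.

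**What to change.** In SAP 9.4 and Tables 56, 57 and 72, define the compared outcome as at least one AE of Grade 3 or higher, and state that a Grade 5 AE counts as an event. Show Grades 3, 4 and 5 as separate descriptive rows, and keep a Grade 3–4 row descriptively to match the protocol's wording.

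The cost is small: one changed filter and no new data. The stated rates will be slightly higher in both arms. Because the protocol names Grade 3 and 4 in its objectives and in Appendix B 9.4.4, the SAP needs a short note explaining the difference.

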2.2.3 Baricitinib

2.2.3.1 Potential Risks of Baricitinib

Baricitinib is a Janus kinase (JAK) inhibitor indicated for the treatment of adult patients with moderately to severely active rheumatoid arthritis who have had an inadequate response to one or more TNF antagonist therapies.

The US product labeling indicates a boxed warning for the risk of serious infections, malignancies and thrombosis, while warnings and precautions include serious infections, thrombosis, gastrointestinal perforations, abnormal laboratory assessments (potential changes in lymphocytes, neutrophils, hemoglobin, liver enzymes, and lipids), and avoidance with the use of live vaccines.

The Summary of Product Characteristics (SmPC) indicates as special warning and precautions for infections, including TB, hematological abnormalities, viral reactivation, use of live vaccines, increase in blood lipid parameters, increase in hepatic transaminase, malignancy, venous thromboembolism, hypersensitivity, and use of baricitinib with potent immunosuppressive medications.

Baricitinib has an established safety profile with a positive benefit/risk profile in rheumatoid arthritis. An integrated analysis of patients with active RA exposed to baricitinib with 3770 patients and 10,127 patient years for a maximum exposure of 7 years (as of February 2018) was recently published (38). No significant differences were seen for baricitinib 4-mg vs placebo in adverse events leading to permanent drug discontinuation, death, malignancy, serious infection, or major adverse cardiovascular events. Incidence rates for deep vein thrombosis/pulmonary embolism were numerically higher in baricitinib 4-mg vs placebo; Incidence rates were similar by dose in 2-mg/4-mg-extended dataset. Malignancy (excluding non-melanoma skin cancer) Incidence rates were 0.8 (2-mg) and 1.0 (4-mg; as-randomized analysis). Fewer than 1% of patients discontinued due to abnormal laboratory results. The frequency of Herpes zoster was higher for baricitinib 4-mg vs placebo (1.4 vs 0.4) baricitinib 4-mg vs 2-mg (1.4 vs 1.0).

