8.3.2 Definition of Serious Adverse Event (SAE)

An AE or suspected adverse reaction is considered serious (i.e., is an SAE) if, in the view of either the investigator or the Sponsor, it results in any of the following outcomes:

- Death;
- A life-threatening AE;
- Inpatient hospitalization or prolongation of existing hospitalization;
- A persistent or significant incapacity or substantial disruption of the ability to conduct normal life functions; or
- A congenital anomaly/birth defect.

Grade 4 AEs (potentially life-threatening events) are not always SAEs unless they are imminently life threatening.

Important medical events that may not meet the above criteria may be considered serious when, based upon appropriate medical judgment, they may jeopardize the subject and may require medical or surgical intervention to prevent one of the outcomes listed in this definition. Examples of such medical events include allergic bronchospasm requiring intensive treatment in an emergency room or at home, blood dyscrasias, convulsions that do not result in inpatient hospitalization, or the development of drug dependency or drug abuse.

“Life-threatening” refers to an AE that at occurrence represents an immediate risk of death to a subject. An event that may cause death if it occurs in a more severe form is not considered life-threatening. Similarly, a hospital admission for an elective procedure is not considered a SAE.

All SAEs, as with any AE, will be assessed for severity and relationship to study intervention.

All SAEs will be recorded on the AE CRF and reported to DMID (see Section 8.3.6).

All SAEs will be followed through resolution or stabilization by a licensed study physician (for IND studies, a physician listed on the Form FDA 1572 as the site PI or Sub-Investigator).

All SAEs will be reviewed and evaluated by DMID and will be sent to the DSMB (for periodic review), and the IRB/IEC.

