8.3.5.1 Investigator Reporting of AEs

Information on AEs will be recorded on the appropriate CRF. All clearly related signs, symptoms, and results of diagnostic procedures performed because of an AE should be grouped together and recorded as a single diagnosis. If the AE is a laboratory abnormality that is part of a clinical condition or syndrome, it should be recorded as the syndrome or diagnosis rather than the individual laboratory abnormality. Each AE will also be described in terms of duration (start and stop date), severity, association with the study product, action(s) taken, and outcome.

Any new infection that occurs on study, regardless of infecting agent (i.e., viral or non-viral) will be captured if it is a Grade 3 or 4 AE or SAE. Completion of the Infection Follow-up eCRF page is required for each infection reported as an adverse event or SAE with site of infection and source of culture provided, if available. The purpose is to document the occurrence of new infections by type of infection and not the duration of the new infections. Therefore, capture the first positive result(s) for the new infection (e.g., blood or urine culture, molecular diagnostic test result, etc.); there is no need to capture repeatedly positive results unless there is a new pathogen identified from the same site (e.g., blood) during the infection event. The sponsor will identify infections considered to be opportunistic based on Winthrop et al. 2015.

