N = Number of Subject in the As Treated Population and specified actual disease severity stratum. n = Number of subjects in a given treatment group who experienced the specified safety event outcome. 95% CI calculated using C-P/Blaker method P-value calculated using Barnard's Exact Test							

Table 73: Analysis of Time to Death, SAEs, or Grade 3 or 4 AEs by Treatment Group – As Treated Population

Actual Disease Severity	Treatment Group	n	Median Time		HR		P-value
			Estimate	95% CI	Estimate	95% CI	
Any Severity (N=X)	Baricitinib + RDV (N=X)	X	x.x	x.x, x.x	x.xx	x.xx, x.xx	x.xxx
	Placebo + RDV (N=X)	X	x.x	x.x, x.x			
Moderate (N=X)	Baricitinib + RDV (N=X)	X	x.x	x.x, x.x	x.xx	x.xx, x.xx	--
	Placebo + RDV (N=X)	X	x.x	x.x, x.x			
Severe (N=X)	Baricitinib + RDV (N=X)	X	x.x	x.x, x.x	x.xx	x.xx, x.xx	--
	Placebo + RDV (N=X)	X	x.x	x.x, x.x			

N= Number of subjects in the As Treated Population and specified actual disease severity stratum.

n = Number of subjects who died or experienced SAEs or Grade 3 or 4 AEs.

HR is the ratio of the hazard of Death/SAE/AE of Grade 3 or 4 in each treatment group estimated from the stratified Cox model. The ratio is Baricitinib + RDV to Placebo + RDV. P-value calculated using the Log-rank test

Table 74: Infections by Treatment Group – As Treated Population, Moderate Disease Severity

Anatomical Location	Pathogen	Baricitinib + RDV (N=X)									Placebo + RDV (N=X)								
		Severe			Life-Threatening			Death			Severe			Life-Threatening			Death		
		n	%	Events	n	%	Events	n	%	Events	n	%	Events	n	%	Events	n	%	Events
Any Location	Any Pathogen	x	x	x	x	x	X	x	x	x	x	x	x	x	x	x	x	x	x
Location 1	Any Pathogen	x	x	x	x	x	X	x	x	x	x	x	x	x	x	x	x	x	x
	Pathogen 1	x	x	x	x	x	X	x	x	x	x	x	x	x	x	x	x	x	x
	Pathogen 2	x	x	x	x	x	X	x	x	x	x	x	x	x	x	x	x	x	x
Location 2	Any Pathogen	x	x	x	x	x	X	x	x	x	x	x	x	x	x	x	x	x	x
	Pathogen 1	x	x	x	x	x	X	x	x	x	x	x	x	x	x	x	x	x	x
	Pathogen 2	x	x	x	x	x	X	x	x	x	x	x	x	x	x	x	x	x	x

Note: Percents may not add to 100 because participants may have infections with multiple pathogens. All Grade 3 or 4 infections are also reported as AEs.
 N=Number of participants randomized to Treatment group.
 n=Number of participants with infection.

Tables with similar format:

Table 75: Opportunistic Infections by Treatment Group – As Treated Population, Moderate Disease Severity

Table 76: Infections by Treatment Group – As Treated Population, Severe Disease Severity

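### The SAP's dedicated infection tables (Tables 74-79) have no any-infection count, no column for serious infections below Grade 3, and no between-arm difference

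*SAP*

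**What the plan says.** **Why infections get their own form.** Protocol Appendix B 2.2.3.1 states: "The US product labeling indicates a boxed warning for the risk of serious infections, malignancies and thrombosis". Appendix B 8.3.5.1 then sets out separate infection reporting. A new infection "will be captured if it is a Grade 3 or 4 AE or SAE", and "Completion of the Infection Follow-up eCRF page is required for each infection reported as an adverse event or SAE". For the organism, sites are told to "capture the first positive result(s) for the new infection (e.g., blood or urine culture, molecular diagnostic test result, etc".

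**Seriousness.** Appendix B 8.3.2 lists, among the criteria, "Inpatient hospitalization or prolongation of existing hospitalization". That criterion does not depend on grade.

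**What the SAP reports.** Section 9.4 says "A summary of the infections reported on the AE CRF will be summarized by treatment group and disease severity (Table 74", and adds: "The anatomical location(s) of the infection and causative pathogen(s) determined by culture will be summarized". Opportunistic infections identified by the sponsor are included. In Appendix 1, the Table 74 shell gives n, percent and events under Severe, Life-Threatening and Death for each arm, by anatomical location and pathogen, with a top row for any location and any pathogen. Tables 75-79 repeat the format for opportunistic infections, the severe stratum and all subjects. The titles say As Treated, but the Table 74 footnote says "N=Number of participants randomized to Treatment group".

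**The concern.** Serious infection is one of the three harms named in the boxed warning. The protocol's amendment history records that the infection-reporting wording was added at the FDA's request. A reader of the report will want two figures: how many participants in each arm had an infection, and how far the arms differ. Tables 74-79 supply neither. They also leave out one kind of infection that the protocol takes care to collect. Three small columns per arm without a total or a contrast make a real excess easier to miss, and make an apparent balance easier to over-read.

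**Working it through.** The point rests on no figure stated in the plan. The check sets the shells beside the capture rules.

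**1. Captured against displayed.** Captured (Appendix B 8.3.5.1): Grade 3, Grade 4, or an SAE of any grade. Displayed (Table 74): Severe (Grade 3), Life-Threatening (Grade 4), Death (Grade 5). Fatal infections are SAEs, so they are in both. The difference is SAEs below Grade 3. Such events can arise, because prolonged hospitalization makes an event serious whatever its grade. Appendix B 8.3.5 confirms that all SAEs are recorded in addition to Grade 3 and 4 AEs.

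**2. Participants infected per arm.** Let S, L and D be the participant counts in the three columns of the top row. Let M be the number with at least one infection of Grade 3 or worse. Table 74 defines n as participants with infection and does not say whether someone with infections of two grades is counted once or twice. From the table alone:

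max(S, L, D) ≤ M ≤ S + L + D

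With invented counts of 40, 15 and 10, M lies between 40 and 40 + 15 + 10 = 65. The sum is exact only if each participant is counted once, at the worst grade. The SAP says maximum severity where it means it (Figure 40 in section 9.3; Table 80 in section 9.6), but not here. The footnote that percentages may not add to 100 concerns multiple pathogens, not multiple grades. Participants whose only infection was an SAE below Grade 3 would come on top of M and are not shown. Table 78 does not help: it pools the disease-severity strata, not the infection grades.

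**3. Between-arm contrast.** Table 57 gives risk differences with 95% CIs for AEs, related AEs, Grade 3-4 AEs, SAEs, fatal SAEs and discontinuations. It has no infection row. Table 72 compares Grade 3 or 4 AEs and SAEs with Barnard's exact test and has no infection row. Renal and hepatic AEs (Tables 61-62) at least have an any-event row with one n per arm across grades.

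**4. Other outputs that include infections.**

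| Output | What it gives | What it lacks |
|---|---|---|
| SAP 9.3 summary of all AEs by system organ class and preferred term, per arm | Could show participants with any infection AE | No table number or shell; no difference or interval |
| Table 58 | Terms reaching 5% | Infections split by preferred term |
| Table 63 | Related AEs by class and term | Related events only |
| Tables 56, 57, 72 | Overall SAE counts | Infections not separated |
| Listing 14 | Non-fatal SAEs by subject | No per-arm count |
| Listing 15 | Infections by subject, with linked AE number | No grade or seriousness field |

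A per-arm count of serious infections could be built by linking Listing 15 to the AE data, but no output plans it.

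**5. Two smaller mismatches.** The Table 74 footnote uses a randomized denominator under an As Treated title. SAP 6.3 and 9.3 point to the treated population for safety. The section 9.4 sentence speaks of pathogens found by culture, while the protocol collects molecular results as well.

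**The case against.** The strongest reply is that infections are AEs and are already covered. Section 9.3 promises all AEs by class and term for each arm, the SAE rows carry an interval and a test, and the listings hold every case. Several stronger readings are indeed tempting, and the documents do not support them:

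- *Tables 74-79 are the only planned analysis of infections.* They are the only dedicated tables; the outputs in step 4 also cover infections. The boxed warning also names malignancies and thrombosis, so infection is not its sole subject.
- *Serious infections below Grade 3 drop out of the report.* They leave Tables 74-79 only. They remain in the SAE rows of Tables 56, 57 and 72, in the Table 73 composite and in the listings. They may also be few: the protocol's fallback definition of Grade 3 (Appendix B 8.3.4.1) includes events that significantly affect clinical status, so many infections that prolong a stay could be graded 3. The documents give no share.
- *Participants will be double counted.* This is possible but not shown. Section 9.3 says each subject is counted once for AE incidence; it does not say in which grade column.
- *Infections found by PCR have no pathogen row.* The restriction to culture is in one sentence of section 9.4. The shell and Listing 15 say only pathogen.

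The manufacturer's Addendum SAP is to pre-specify additional safety analyses (SAP 2.1) and may include an infection contrast. It is not among these documents, so the statement that none is planned applies to this SAP. Section 17 allows extra tables, but permission is not pre-specification.

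What stands is that none of these outputs gives an any-infection or serious-infection estimate by arm with an interval for the difference.

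**Conclusion.** The concern holds in this limited form. As written, the dedicated tables omit a category of infection that the protocol collects, and they do not determine the number of participants infected. This SAP plans no between-arm estimate for a boxed-warning risk. The effect cannot be put in patients or percentage points, because the documents give neither an infection rate nor the proportion of serious infections below Grade 3. The counts in step 2 only illustrate the bound. The conclusion rests on reading the shells literally and on the absence of an infection row from Tables 57 and 72. It should be corrected before reporting; it does not affect the efficacy analysis or the conduct of the trial.

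**What to change.** **Table 57:** add three rows, each with risk difference and 95% CI: at least one infection (Grade 3/4 or SAE), at least one serious infection, and at least one opportunistic infection.

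**Tables 74-79:** add an any-infection column that counts each participant once; state that the severity columns count each participant at maximum grade; add a column for SAEs below Grade 3; define N as the As Treated population.

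**SAP 9.4:** align the pathogen sentence with the protocol, so that it covers culture or molecular results.

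**Cost:** SAP wording and table shells only. The data are already on the AE and Infection Follow-up forms. The downside is a few more descriptive rows without multiplicity control, which the SAP should label as descriptive.
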